9.1.2.2 Efficacy Review

9.2 Assessment of Safety

Safety will be assessed by the recording of adverse events, vital signs, changes in physical exam, 12-lead ECGs and the following clinical laboratory tests:

- **Hematology**

Hemoglobin (Hgb)	Hematocrit (Hct)
Platelet count	Red blood cell count
White blood cell count with differential	

- **Chemistry**

Urea	Creatinine
Total bilirubin	Alkaline Phosphatase
Aspartate transaminase (AST)	Alanine transaminase (ALT)
Gamma-glutamyl transferase (GGT)	Lactic dehydrogenase (LDH)
Glucose	Albumin
Total protein	Bicarbonate
Phosphate	Sodium
Potassium	Chloride
Calcium	Amylase

- **Coagulation:** INR, APTT

- **Urinalysis**

pH	Specific gravity
Protein	Glucose
Ketones	Bilirubin
Blood	Nitrites
Leukocytes	Urobilinogen
Microscopic urine analysis	

9.2.1 Adverse Events

NOTE: The content of this section is based on the FDA “Guidance for Industry and Investigators; Safety Reporting Requirements for IND and BA/BE Studies” issued in December 2012. A copy of this guidance will be provided in the to the site upon request and should be referred to if and when the following do not provide sufficient guidance for an investigator to make an assessment regarding the occurrence, severity, relationship and expectedness of an adverse event (AE).

Adverse event solicitation and recording will begin immediately upon start of dosing with the study product (VGT-309) and will include only on-treatment (treatment-emergent) events. Any changes to a subject’s health that occur between the signing of the informed consent and start of dosing will be recorded as updates to the subject’s medical history.

Subjects will be instructed to report AEs during the study and staff will query subjects regarding AEs throughout the study. The Investigator (and/or designee) must document all AEs reported from the time of dosing through completion of the End-of-study Visit (Days 25 -35). Any subject who is withdrawn from the study due to an AE shall be followed until the event has resolved or stabilized or 30 days after last dose and the Investigator will document available follow-up information on the subject’s source documentation and CRF.

9.2.1.1 Definition of an Adverse Event

The FDA Safety Guidance, referencing 21CFR312.32(a), defines an Adverse Event as follows:

Adverse event means any untoward medical occurrence associated with the use of a drug in humans, whether or not considered drug related.

An adverse event (also referred to as an adverse experience) can be any unfavorable and unintended sign (e.g., an abnormal laboratory finding), symptom, or disease temporally associated with the use of a drug and does not imply any judgment about causality. An adverse event can arise with any use of the drug (e.g., off-label use, use in combination with another drug) and with any route of administration, formulation, or dose, including an overdose.

Adverse Events are **NOT**:

- Medical or surgical procedures (e.g., surgery, endoscopy, tooth extraction, transfusion). The *condition* that leads to the procedure is the AE.
- Situations where an untoward medical occurrence has not occurred (e.g., hospitalization for elective surgery, social and/or convenience admissions).

9.2.1.2 Evaluating and Reporting of Adverse Events

All AEs (i.e., a new event or an exacerbation of a pre-existing condition) that occur after the start of dosing with VGT-309 and through the end of the study - as evaluated in the End-of-Study Visit (Days 25 – 35) - or, if the subject is withdrawn due to an AE, must be recorded as an AE or SAE (if applicable), on the Adverse Event eCRF. The Investigator must follow all AEs until the AE resolves, or until the Investigator and/or the Medical Monitor determine the event is chronic or clinically stable. If an AE remains unresolved at the conclusion of the study, the Investigator and Medical Monitor will make a clinical assessment to determine whether continued follow-up of the AE is warranted. All subjects who have received any exposure to VGT-309 (even if dosing is not completed) must be evaluated for AEs.

The Investigator should attempt to establish a diagnosis of the event based on signs, symptoms and/or other clinical information. In such cases, the diagnosis should be documented as the AE and not the individual signs/symptoms.

All AEs or SAEs must be promptly documented on the Adverse Event eCRF and assessed by the Investigator. Details of the event must include the dates of onset and resolution, severity, relationship to study drug, seriousness, and whether the event caused the subject to withdraw from the study, outcome and timing with regard to administration of the study drug.

Grade: Each AE will be assigned a “Grade” based on the Common Terminology Criteria for Adverse Events (CTCAE). Version 5.0 of the CTCAE will be used for this study. Refer to Section 9.1.2 for stopping rules based on the assigned Grade of AE.

Severity: Severity should be graded and recorded as follows:

- Mild: Awareness of event but easily tolerated.
- Moderate: Discomfort enough to cause interference with usual activity.
- Severe: Inability to carry out usual activity, incapacitating, requires medical intervention.

Relationship: The relationship of the Adverse Event to the study drug will be determined by the Principal Investigator, and assessed using the following definitions:

- **Related:** There is a distinct temporal relationship between the event onset and administration of the study drug. There is a known reaction to agent or chemical group or predicted by known pharmacology. The event cannot be explained by subject’s clinical state or other factors.
- **Unrelated:** Evidence exists that the AE has an etiology other than the study drug (e.g., pre-existing condition, underlying disease, intercurrent illness, or concomitant medication).

These criteria, in addition to good clinical judgment, should be used as a guide for determining the causal assessment.

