10.3.1	Treatment Comparisons	18
10.3.2	Primary Hypothesis	18
10.4	SAFETY ANALYSIS	19
10.4.1	Adverse Events	19
10.4.2	Clinical Laboratory Data	19
10.4.3	Other Safety Evaluations	19
11.	RECORDING AND COLLECTION OF DATA	19
11.1	CASE REPORT FORM	19
11.2	STUDY FILES AND SUBJECT SOURCE DOCUMENTS	20
11.3	MONITORING	20
11.4	AUDIT	20
11.5	RETENTION OF DATA	21
12.	PUBLICATION POLICY AND SHARING OF DATA.....	21
ATTACHMENT A: Schedule of Assessments		22
ATTACHMENT B: Summary of Changes		23

Study Synopsis

Sponsor	Vergent Bioscience, Inc. [REDACTED]
Title	A Phase 2, Multi-center, Open-label Study to Evaluate the Safety and Efficacy of VGT-309, a Tumor-Targeted, Activatable Fluorescent Imaging Agent, in Subjects Undergoing Surgery for Cancer in the Lung
Protocol Number	VGT-309-2B-2023
Lead Clinical Investigator	[REDACTED]
Study Centers	Up to 7 Centers in the US and Australia
Investigational Medicinal Product (IMP) (also referred to as Study Drug)	VGT-309 for Injection, 10 mg/vial
Primary Efficacy Objective	Assess the efficacy of VGT-309 with near-infrared (NIR) imaging for lesion visualization when compared to standard surgical techniques in subjects undergoing surgery for proven or suspected cancer in the lung.
Secondary Efficacy Objective	Assess the utility of VGT-309 with NIR imaging to identify cancerous tissue as confirmed by histopathology.
Safety Objective	Determine the safety and tolerability of VGT-309 in subjects with proven or suspected cancer in the lung.
Introduction and Rationale	[REDACTED]

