VGT-309 Dosing	
The dose for this study is 0.32 mg/kg of VGT-309 and [REDACTED]. Based on ongoing investigations and after review by the DSC this dose may be modified.
 
[REDACTED]

Data Safety Committee (DSC)	
A Data Safety Committee will be appointed by Vergent Bioscience and will include at a minimum:
 
[REDACTED]

Enrollment Period	It is expected that the time required to enroll 100 subjects in this study will be approximately 8 months.
Study Duration	Each subject may expect to be on study for up to 65 days: 

Primary Efficacy Assessments	
In vivo, intra-operatively:
 
 • Use of white light and/or palpation followed by NIR imaging for localization of preoperatively identified lung lesion(s), potential synchronous or occult malignant lung lesion(s), and potential cancer-containing lymph nodes. 
Ex vivo, in the operating room:
 
 • NIR imaging to determine fluorescence proximity to closest resection margin. 
Ex vivo pathology
 
 • Histologic examination of resected tissues.
Secondary Efficacy Assessments	Comparison of NIR imaging, conducted both inside and outside the subject, to results of histologic examination.
Safety Assessments	
 • Treatment-emergent adverse events • Clinical laboratory assessments of blood and urine (See section 9.2.3 for details): 
 ○ Hematology Panel ○ Coagulation – INR and aPTT ○ Chemistry Panel including liver function tests (LFTs) and amylase ○ Urinalysis with microscopy • Pre- and post-dose ECGs (in triplicate) • Vital signs (BP, HR, temp, resp) • Additional studies if identified during the trial as being necessary to adequately assess safety

	
Pregnancies that occur between dosing and Day 30 will be followed until 6 weeks after delivery or termination of the pregnancy.
 
(Refer to Schedule of Assessments for details)

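### The causality definitions leave a novel, unexplained event after VGT-309 in neither category when read literally, and they mix expectedness into relatedness

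*Protocol*

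**What the plan says.** Protocol 9.2.1.2 says that relationship to study drug "will be determined by the Principal Investigator, and assessed using the following definitions". Two categories follow.

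- Related has three sentences in a row: a distinct temporal relationship to dosing; "There is a known reaction to agent or chemical group or predicted by known pharmacology"; and no explanation in the subject's clinical state or other factors. No connective links them.
- Unrelated applies when "Evidence exists that the AE has an etiology other than the study drug".

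There is no intermediate category and no default for an undetermined event. The protocol adds: "These criteria, in addition to good clinical judgment, should be used as a guide for determining the causal assessment". SAP 10.1.3 repeats both definitions without that sentence. It adds that an event with no recorded relationship is counted as related in summaries and shown as missing in listings.

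Protocol 9.2.1 names an FDA safety-reporting guidance, supplied to sites on request, for use when the protocol text is not enough to "make an assessment regarding the occurrence, severity, relationship and expectedness of an adverse event". Protocol 9.2.2.1 provides for suspected unexpected serious adverse reactions (SUSARs) to be sent to all sites. The synopsis gives the study centers as "Up to 7 Centers in the US and Australia".

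**The concern.** A safety objective for an investigational imaging agent includes finding reactions that nobody predicted. A definition of Related that lists a known or predicted reaction as one of its parts handles exactly those events badly. An investigator who applies the text strictly cannot call such an event Related, and cannot call it Unrelated without evidence of another cause.

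The call has consequences. Both pause triggers visible in Protocol 9.1.2.1 depend on it: a serious event judged related, or an event above Grade 2 attributed to VGT-309. So do the distribution of related SAEs to all sites (Protocol 9.2.2.1) and the treatment-related tables (Protocol 10.4.1; SAP 10.1 and 10.1.5).

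**Working it through.** The plan states no figure on this point, so the check is mainly a logical one.

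**Step 1. Test event.** Take an event soon after dosing, of a kind not known for the agent or its class and not predicted by its pharmacology, with no other cause found.

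| Statement | Met? |
|---|---|
| Related: distinct timing | Yes |
| Related: known or predicted reaction | No |
| Related: not otherwise explained | Yes |
| Unrelated: evidence of another cause | No |

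The event meets 2 of the 3 Related statements and does not meet the Unrelated requirement.

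**Step 2. Effect of the missing connective.** If all three Related statements are required, which is the natural reading of a definition written this way, the event fits neither category. If they are alternatives or considerations, it is Related. The text does not say which applies.

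**Step 3. Consistency within the protocol.** Section 9.2.1 lists relationship and expectedness as two separate assessments. Section 9.2.2.1 provides for reactions that are suspected and also unexpected. If all three statements are required, an event that is neither known nor predicted can never be Related, which leaves little room for the SUSAR provision. Expectedness has been placed inside causality.

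**Step 4. What the softening provisions do.**

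- The clinical-judgment sentence lets an investigator choose Related. It does not say that the known-or-predicted statement may be set aside, and the SAP leaves the sentence out.
- The FDA guidance is a named fallback. Its content is not in these documents, so whether it settles the test event cannot be judged here.
- The SAP rule counts a blank field as related in summaries. It does not apply once Unrelated has been recorded, and it has no bearing on the pause trigger.

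**Step 5. Where the call still matters.**

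- Serious events: all are reported to the sponsor within 24 hours regardless of causality (Protocol 9.2.2.1), and a complication that prolongs hospitalization is serious (9.2.2). The sponsor sees these whatever the label.
- Non-serious events above Grade 2: in the visible text of 9.1.2.1 the only trigger is attribution to VGT-309, and one event in one subject is enough. A single call can therefore decide whether the discretionary pause review is prompted.
- Treatment-related tables: with about 100 subjects enrolled (Protocol 5.1), and taking all as dosed, one subject classed differently moves an incidence by 1/100 = 1.0 percentage point.

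No event rate is given for novel or undetermined events, so no expected number of affected subjects can be calculated.

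**The case against.** The best counter-argument is that the protocol disclaims a rigid reading. It calls the criteria a guide to be used with clinical judgment, and a protocol that provides for SUSARs cannot plausibly intend that every related event be known already. That is a fair account of intent, and it means an investigator can reach Related for the test event. It does not make the definition say so.

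It can also be said that known pharmacology is a legitimate causality consideration. It is. The difficulty is only that it stands as part of the definition and is not marked as supporting evidence.

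The safeguards outside the definition are real. "All AEs or SAEs must be promptly documented on the Adverse Event eCRF and assessed by the Investigator", so the event is recorded under either label. On dosing, the synopsis says "Based on ongoing investigations and after review by the DSC this dose may be modified", with no attributed event required. The sponsor may stop the study for any reason (Protocol 7). Qualifying Day 3 laboratory events get repeat blood draws with no attribution condition stated in 6.1.6, although 9.2.3.1 cannot be read in the available text. Parts of the DSC description are redacted, so a routine review that would catch unattributed events cannot be excluded.

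A reader might infer two stronger things. One is that drug reactions will be under-attributed. The documents do not support this: nothing directs an undetermined event to Unrelated, and the SAP rule for blank fields leans the other way. The other is that centers will classify the same event differently. The text leaves room for that, but causality calls always involve judgment, and nothing here shows a difference between centers or that new wording would remove one.

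**Conclusion.** The definition is faulty as written in both documents. Read literally, it gives a novel, unexplained event no category, and it makes expectedness part of causality although Protocol 9.2.1 treats the two separately. The conclusion rests on reading the three Related statements as jointly required, which is natural but not stated; on the looser reading the fault is an ambiguity.

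The consequence is limited. It is confined mainly to the discretionary pause trigger for non-serious events above Grade 2 and to the treatment-related tables, at about 1 percentage point per reclassified subject if about 100 are dosed. Frequency is unknown. This is a cheap improvement to make, not evidence that safety signals would be lost.

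**What to change.** In Protocol 9.2.1.2 and SAP 10.1.3:

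1. Define Related as a reasonable possibility that VGT-309 caused the event.
2. State that timing, known or predicted pharmacology and the absence of another explanation are supporting considerations that need not all be met.
3. State that an event with a plausible temporal relationship to dosing and no other identified cause is classed as Related, and that surgery and anesthesia count as possible other causes. This matters because resection follows dosing by 12 to 36 hours (Protocol 3); without it, ordinary post-operative complications could default to Related.
4. Carry the clinical-judgment sentence into the SAP so that the two documents match.

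The cost is wording in the protocol, the SAP and the eCRF completion guidelines. Endpoints, sample size and visits do not change. The downside is that somewhat more events will be labelled related and sent for discretionary DSC review, some of them post-operative events whose cause cannot be settled.

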9.2.2 Serious Adverse Events (SAEs)

All SAEs as defined below that occur after the start of dosing of VGT-309 and through the End-of-Study Visit (Days 25 – 35) must be reported to Vergent as soon as the site becomes aware of them. Any SAEs occurring more than 30 days after last study drug administration and considered drug-related must also be reported.

An SAE is an AE from this study that results in any of the following outcomes:

- Death.
- Life-threatening situation (subject is at immediate risk of death).
- Inpatient hospitalization or prolongation of existing hospitalization.
- Persistent or significant disability/incapacity.
- Congenital anomaly/birth defect in the offspring of a subject who received study drug. (Refer to Section 9.2.4 for reporting of pregnancy)

NOTE: Important medical events that may not result in death, be immediately life-threatening, or require hospitalization, may be considered an SAE when, based upon appropriate medical judgment, they may jeopardize the subject *and* may require medical or surgical intervention to prevent one of the outcomes listed in this definition.

A life-threatening AE is defined as any adverse experience that places the subject in the view of the Investigator, at immediate risk of death from the event as it occurred. This does not include an event that might have led to death *if* it had occurred with greater severity.

“Inpatient hospitalization” means the subject has been formally admitted to a hospital for medical reasons, for any length of time. Presentation and care within an emergency department does not necessarily constitute an SAE. Complications that occur during hospitalization are AEs. If a complication prolongs hospitalization, it is an SAE.

All deaths, regardless of cause, must be reported for subjects on study (within 30 days of last study drug dose). The SAE term should reflect the event that leads to the death with “death” recorded as the outcome

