6.1.7 Day 25 - 35: End of Study Follow up -OR- Early withdrawal

This visit may be conducted in clinic or by telehealth visit. During this visit or if the subject withdraws from the study early, the following assessments will be done:

1. Review of concomitant medications for changes since last visit.
2. Observation for and solicitation of adverse events.
3. Blood draw ONLY to assess a laboratory value that did not return to baseline after the Day 7-14 draw (See Sections 6.1.6 and 9.2.3.1)

Following completion of these assessments, subjects will be released from the study. Additional follow-up may be necessary if an SAE is reported and has not yet resolved (See Section 10.2.2 for details).

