9.2.4 Pregnancy Reporting

Pregnancy is not considered an AE. Nevertheless, any pregnancy that occurs between dosing and as evaluated in the End-of-Study Visit (Days 25 – 35), should be verified and recorded. Sites should complete the Pregnancy Form provided by Vergent, and submit it to the Vergent Safety Mailbox ([contact]) within 24 hours of knowledge. Subjects or their female partner will sign a separate consent form allowing the Study Site and Sponsor to follow up with them through 6 weeks post-delivery or termination of the pregnancy.

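### The two SAE reporting rules do not meet: a non-fatal SAE after an early End-of-Study Visit but within 30 days of dosing falls under neither

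*Protocol*

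**What the plan says.** Protocol 9.2.2 sets two windows for SAEs. The first covers SAEs of any cause that "occur after the start of dosing of VGT-309 and through the End-of-Study Visit (Days 25 – 35) must be reported to Vergent". The second covers drug-related events only: "Any SAEs occurring more than 30 days after last study drug administration and considered drug-related must also be reported".

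The same section has a separate rule for deaths: "All deaths, regardless of cause, must be reported for subjects on study (within 30 days of last study drug dose".

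The surrounding sections end collection at the same visit. Under Protocol 9.2.1 the investigator "must document all AEs reported from the time of dosing through completion of the End-of-study Visit (Days 25 -35", and 9.2.1.2 likewise stops recording at that visit. Protocol 6.1.7 then closes the subject's participation: "Following completion of these assessments, subjects will be released from the study". The later follow-up it mentions is for an SAE already reported and not yet resolved.

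Pregnancy has two windows. The synopsis (Safety Assessments) says: "Pregnancies that occur between dosing and Day 30 will be followed until 6 weeks after delivery or termination of the pregnancy". Protocol 9.2.4 instead covers "any pregnancy that occurs between dosing and as evaluated in the End-of-Study Visit".

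The SAP repeats the SAE definition (10.1.4) and sets no reporting window.

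**The concern.** The first SAE rule stops at a date that differs between subjects, and the second starts at a fixed point after dosing. They join only if the visit takes place at least 30 days after dosing, and the protocol allows it earlier. A drug-related serious event can then carry no stated duty in the last days of the month after dosing and become reportable again from day 31. That ordering can hardly be intended.

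Elsewhere the protocol treats about 30 days as its safety horizon: contraception runs to Day 30, the synopsis counts pregnancies to Day 30, and deaths are reportable for 30 days after the dose.

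The consequence is for safety oversight. Under Protocol 9.1.2.1 a related SAE may pause the study and goes to the Data Safety Committee; under 9.2.2.1 it is sent to every site. An event that nobody is told to report may reach neither. SAP 10.1 defines treatment-emergent events with no end date, so an event in the gap would qualify for the safety tables although collection has stopped. No efficacy endpoint, analysis population or test is affected.

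**Working it through.** The plan states no figure to reproduce. The check is calendar arithmetic.

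**Inputs**
- All-cause SAE rule ends at the End-of-Study Visit, Days 25 to 35 (Protocol 9.2.2).
- Drug-related rule starts more than 30 days after the last dose (Protocol 9.2.2). There is one dose.
- Day origin: Protocol 6.1.3 makes dosing Day 1. Protocol 3, the synopsis and SAP 4 count the final visit from surgery. Sections 9.2.1 to 9.2.4 name no origin.
- Dosing to surgery: 12 to 36 hours, that is 0.5 to 1.5 days (Protocol 3).

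**Formula.** Uncovered days = max(0, 30 − days from dosing to the visit). For a visit labelled Day D, the days from dosing are D − 1 if dosing is Day 1, D if the label means days after dosing, and D + 0.5 to D + 1.5 if it means days after surgery.

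| Visit day D | Dosing is Day 1: 30 − (D − 1) | Days after dosing: 30 − D | Days after surgery: 30 − (D + 1.5) to 30 − (D + 0.5) |
|---|---|---|---|
| 25 | 6 | 5 | 3.5 to 4.5 |
| 26 | 5 | 4 | 2.5 to 3.5 |
| 27 | 4 | 3 | 1.5 to 2.5 |
| 28 | 3 | 2 | 0.5 to 1.5 |
| 29 | 2 | 1 | 0 to 0.5 |
| 30 | 1 | 0 | 0 |
| 31 to 35 | 0 | 0 | 0 |

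The gap exists under every origin; only its length and the last affected visit day change. The synopsis gives up to 65 days on study, which equals 30 screening days plus 35 and so fits counting from dosing, but its breakdown is blacked out and does not settle the matter.

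**Early withdrawal.** Protocol 6.1.7 and 7.1 apply the final-visit assessments as soon as possible after withdrawal. If that visit counts as the subject's End-of-Study Visit, the gap is 30 minus the days since dosing. As an illustration, a withdrawal visit 14 days after dosing leaves 30 − 14 = 16 days.

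**Does another section fill the gap?** Protocol 9.2.1 and 9.2.1.2 stop at the same visit. Protocol 9.2.2.1 says how and how fast to report, not over what period. The follow-up in 9.2.1 for subjects withdrawn because of an AE concerns the event that led to withdrawal, not new ones. The death rule covers fatal events only.

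**Pregnancy.** If the visit precedes Day 30, Section 9.2.4 closes earlier than the synopsis; if it follows Day 30, it closes later, by up to 35 − 30 = 5 days.

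**After alignment.** If the all-cause rule ran to the later of the visit and 30 days after dosing, the uncovered interval would be 0 days for every visit day from 25 to 35 under all three origins.

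**The case against.** The best defence is that this is a drafting mismatch which sites would resolve sensibly. Protocol 9.2.2.1 asks for notification within 24 hours of the investigator learning of an SAE, whatever the cause, and repeats no end date. The second SAE rule is plainly meant to extend reporting, and few sites would read it as exempting a related event on day 27 while requiring one on day 31. Few such events are likely with a single dose in about 100 subjects, and Protocol 10.4.1 plans no statistical testing of safety. This limits the practical effect. It does not supply the missing window, since a reporting procedure applies only to events that the rules make reportable.

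Three stronger readings are tempting, and the documents do not support them.

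- **Deaths within 30 days may lawfully go unreported.** A reader might infer this from the on-study qualifier combined with release at the visit. The parenthesis in the death rule more naturally defines on study as within 30 days of the dose, so these deaths are reportable. The weakness is detection: nobody is scheduled to ask after release.
- **A known share of subjects is exposed.** An even spread of visits over the 11 days would give 5/11 = 45% counting days after dosing, or 6/11 = 55% with dosing as Day 1. Nothing in the documents supports an even spread, and the figure moves with the unsettled origin.
- **Unequal follow-up of 25 to 35 days invalidates the safety tables.** This is an ordinary visit window in a single-arm study, and aligning the SAE rules would not remove it.

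**Conclusion.** The concern holds for non-fatal SAEs. As written, an SAE between an early End-of-Study Visit and 30 days after dosing falls under neither reporting rule, even when drug-related. For a scheduled visit on the earliest allowed day the gap is 3.5 to 4.5 days counted from surgery, 5 counted as days after dosing, and 6 with dosing as Day 1. It is longer after early withdrawal if that visit closes the window. For deaths the finding is narrower: the rule exists, but no planned contact would reveal a death after release. For pregnancy, the synopsis and Section 9.2.4 give different end points, a separate and minor inconsistency.

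This rests on a literal reading of Section 9.2.2 and on no window being set in parts that cannot be read in the public copy (the Schedule of Assessments and Section 9.2.3.1). The number of subjects or events affected cannot be estimated from the documents. The point deserves correction because it concerns drug-related serious events and is cheap to close; it does not bear on the efficacy conclusion.

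**What to change.** Reconcile the synopsis (Safety Assessments) with Protocol 9.2.1, 9.2.1.2, 9.2.2 and 9.2.4 so that the windows meet. One wording would require all SAEs *through the later of the End-of-Study Visit and 30 days after dosing*, and drug-related SAEs at any time after that, with the same end point for deaths and pregnancies. State whether the visit days run from dosing or from surgery, and whether an early withdrawal visit closes the reporting window.

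Optionally, for subjects seen before 30 days after dosing, confirm vital status and SAEs by a brief phone or chart check once day 30 has passed. Without it the duty is stated but events after release may still not come to light. The check would add little for pregnancy, because a conception in those last days would rarely be known so soon.

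The cost is a wording change and, if the check is adopted, one short contact for some subjects. No new visit or sample is needed, and the Day 25 to 35 visit window can stay as it is.
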